Endothelial cell perturbation and reduced pulmonary blood flow may be relevant to the pathogenesis of emphysema^{31,32} and important in AATD. AAT has been shown to attenuate endothelial apoptosis in animal models of emphysema.^{33,34} We examined the endothelial hypothesis of emphysema in the MESA COPD Study (AAAD6395), a case-control study of COPD, in which we found pulmonary microvascular blood flow on contrast-enhanced magnetic resonance imaging (MRI) to be inversely associated with CT percent emphysema and COPD stage, and associated with CD31 $^{+}$ endothelial microparticles (EMPs), which reflect endothelial apoptosis.^{35,37} In the Alpha-1 Foundation-funded study “Pulmonary Vascular Damage in Alpha-1 Antitrypsin Deficiency”, which followed the MESA COPD protocol, we found greater CD31 $^{+}$ EMPs in AATD compared to MESA COPD cases and controls, and a non-significant reduction in pulmonary microvascular blood flow in AATD compared to controls. Importantly, those with

AATD on AAT augmentation had lower CD31⁺ EMPs and a trend toward greater pulmonary microvascular blood flow compared to those not on AAT therapy. These findings demonstrate increased endothelial damage in AATD compared to non-AATD COPD and suggest amelioration of endothelial damage by AAT augmentation; however whether AAT augmentation reduces CD31⁺ EMPs and improves pulmonary microvascular blood flow is unknown.

Therefore, we propose to accrue 15 subjects with PiZZ AATD-associated lung disease who are on AAT augmentation therapy into a study protocol that includes: 1) a Phase IIa cross-over randomized controlled trial (RCT) of aspirin vs. placebo and 2) a withdrawal study with a follow-up visit off AAT augmentation therapy in order to test the following hypotheses:

- 1) Randomization to aspirin 81mg daily increases pulmonary microvascular blood flow on MRI and improves secondary endpoints compared to placebo in participants with AATD-associated lung disease receiving standard care (including AAT augmentation therapy).
- 2) CD31⁺ EMPs will be lower and secondary endpoints will be improved when participants are on AAT augmentation therapy compared to off AAT augmentation therapy, while receiving other standard medical treatment.

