Successful completion of these aims would demonstrate that aspirin and AAT augmentation therapy improve pulmonary microvascular blood flow and reduce CD31⁺ EMPs in AATD-related lung disease, would support future studies evaluating aspirin in emphysema in AAT, demonstrate additional benefits of AAT augmentation, and support the use of pulmonary MRI and EMPs as outcomes for clinical trials in COPD.

2. Study Design

- a. The proposed study is a single-center Phase IIa randomized cross-over study and withdrawal study.
- b. The study will accrue 15 subjects and enroll up to 20.
- c. Inclusion criteria:
 - i. Alpha-1 antitrypsin deficiency (PiZZ genotype)
 - ii. 40 years of age or older
 - iii. Evidence of emphysema on CT scan as read by a Radiologist
 - iv. On intravenous alpha-1 antitrypsin replacement therapy
- d. Exclusion criteria:
 - i. Platelet count < 150,000/dL, history of intracranial hemorrhage or severe GI bleed, use of systemic anticoagulant, physician prescribed use of antiplatelet drug (including aspirin and P2Y12 receptor inhibitors), or known severe liver disease;
 - ii. Immunosuppression by use of medications (including oral prednisone) or medical condition (organ transplantation or actively-treated malignancy), including autoimmune conditions that require immunomodulatory treatment (e.g. anti-TNF agents);
 - iii. Known atrial fibrillation or left ventricular (LV) systolic heart failure;
 - iv. Contraindication to MRI, including pregnancy, weight > 300 lbs (due to weight limits of the machine), those with pacemakers, aneurysm clips, cochlear implants or other implanted electronic devices, or severe claustrophobia;

- v. Chronic renal insufficiency (estimated GFR < 45 L/min/1.73 m² or self report) due to slightly increased risk of nephrogenic systemic fibrosis from gadolinium administration and aspirin-related renal insufficiency. GFR will be calculated using the MDRD equation based on the most recent laboratory sample available (within the last 30 days required). If one is not available at the time of MRI a point-of-care Creatinine will be run and this value will be used instead of the laboratory sample;
- vi. Frequent exacerbations of respiratory symptoms (two or more in the last year); and
- vii. Exacerbation of respiratory symptoms within the previous 6 weeks, such as that requiring hospitalization, oral prednisone or antibiotics to control symptoms.

[figure not shown]

Figure 1. Study Design

Table 1: Study Components

Visit #:	1	2	3	4

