Exam component	Screening visit	After treatment 1	After treatment 2	Off AAT augmentation
Anthropometry	X	X	X	X
Blood pressure		X	X	X
Questionnaires	X	X	X	X
Phlebotomy				
Endothelial microparticles		X	X	X
Creatinine, CBC	X	X	X	X
Platelet activation		X	X	X
Alpha-1 antitrypsin level		X	X	X
Urine specimen		X	X	X
Spirometry, pre- and post-bronchodilator	X	X	X	X
Diffusing capacity	X	X	X	X
Pulse oximetry	X	X	X	X
Six minute walk test		X	X	X
Non-contrast chest CT	X			
Cardiopulmonary MRI				
Pulmonary microvascular blood flow		X	X	X
RV, LV, cardiac output		X	X	X

- e. Endpoints
 - i. Aspirin RCT
 - (1) Primary endpoint: pulmonary microvascular blood flow
 - (2) Secondary endpoints:
 - a. Pulmonary perfusion: pulmonary microvascular blood volume, pulmonary microvascular transit time, and above measures of pulmonary perfusion in areas of emphysema on chest CT
 - b. CD31+ endothelial microparticles (reflecting endothelial apoptosis), CD62+ endothelial microparticles (reflecting endothelial activation)
 - c. Spirometry: post-bronchodilator FEV₁ and FEV₁/FVC
 - d. Pulse oximetry
 - e. Diffusing capacity
 - f. Six minute walk test
 - g. Alpha-1 antitrypsin level
 - h. Cardiac MRI: LV EDV, RV EDV, LV SV, cardiac output
 - i. Questionnaire: MMRC dyspnea scale, COPD Assessment Test
 - ii. Alpha1 Augmentation Withdrawal Study
 - (1) Primary endpoint: CD31+ endothelial microparticles (reflecting endothelial apoptosis)
 - (2) Secondary endpoints:
 - a. CD62+ endothelial microparticles (reflecting endothelial activation), platelet microparticles (reflecting platelet activation)
 - b. Pulmonary perfusion: pulmonary microvascular blood flow, pulmonary microvascular blood volume, pulmonary microvascular transit time, and above measures of pulmonary perfusion in areas of emphysema on chest CT
 - c. Spirometry: post-bronchodilator FEV₁ and FEV₁/FVC
 - d. Pulse oximetry
 - e. Diffusing capacity
 - f. Six minute walk test
 - g. Markers of platelet activation: beta-thromboglobulin, platelet factor 4, thromboxane B2, von Willebrand factor
 - h. Cardiac MRI: LV EDV, RV EDV, LV SV, cardiac output
 - i. Questionnaire: MMRC dyspnea scale, COPD Assessment Test

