 - f. Subjects will undergo telephone pre-screening before Visit 1. At Visit 1 they will be consented, after which a platelet count and creatinine will be drawn to confirm eligibility. Participants will then complete questionnaires, perform spirometry, diffusing capacity and pulse oximetry. Eligible patients will then be randomized as to the order of intervention vs. placebo and will undergo non-contrast chest CT. Randomization will be stratified by smoking status with full concealment of allocation; subjects and the investigative team will be blinded as to treatment assignment. The intervention will be 81mg aspirin and a matched placebo, each taken once per day in the morning. Each treatment will last approximately 2 weeks (Figure 1, previous page) with Visits 2 and 3 occurring at the end of treatment 1 and 2, respectively. Each treatment may be continued for up to 18 days, if needed, to coordinate scheduling of the participant visit and procedures. There will be a 2-week washout period between the treatments, and the total length of the randomized protocol will be approximately 6 weeks. The CU Research

Pharmacy will dispense study medications. During the study period, subjects will be asked to continue the same medication regimen and avoid using over-the-counter aspirin and other non-steroidal anti-inflammatory drugs.

- g. Timing with respect to AAT infusions: We will recruit subjects who are on AAT augmentation therapy, and the timing of study visits will be coordinated with their weekly dosing of AAT to minimize differences between study visits other than the intervention. We will schedule patient visits on days 1-3 post-infusion in order to study the effects of peak AAT levels.
- h. Withdrawal of AAT augmentation therapy:
Subjects will be asked to stop AAT augmentation therapy for approximately 5 weeks and return for Visit 4. Withdrawal of AAT for 5 weeks (a maximum of 5.5 weeks) will allow AAT levels to drop briefly to those seen in the absence of AAT augmentation.

3. Statistical Procedures

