- a. Data analysis: Data analysis will be performed primarily by the PI at Columbia University. The primary analysis will use paired t-tests to compare pulmonary microvascular blood flow on aspirin compared to placebo, and CD31⁺ EMPs on AAT augmentation therapy compared to off augmentation following the intention-to-treat principle. Similar analyses will be performed for secondary endpoints. Exploratory analyses will also evaluate for different effects in subgroups by smoking status, COPD severity, use of supplemental oxygen, and by severity of reduction in DLCO and will evaluate for period and carryover effects. Approaches to missing data will include: 1) minimization through short study duration and efforts to retain 100% of participants for 3 months and 2) sensitivity analyses using a variety of imputed values (worst-case scenario, baseline observation carried forward, last observation carried forward).
- b. Statistical power: Power was estimated for a paired t-test to compare an individual's pulmonary microvascular blood flow before and after the intervention. For 15 subjects with power of 80% and $\alpha=0.05$, we will be able to detect a minimally significant difference of 0.30 log CD31⁺ EMPs (1.2 SDs of the difference in log CD31⁺ EMPs for those on replacement and not), and a minimally significant difference of 48.4 mL blood/min*100mL lung (1.6 times the SD of the difference in pulmonary microvascular blood flow [PMBF] for those on replacement and not). Power will be adequate for CD31⁺ EMPs and moderate for PMBF. As power was derived from a cross-sectional analysis, this is a conservative estimate and we expect that power will be improved when comparing changes within an individual.

4. Recruitment and Consent

- a. Recruitment: Participants will be recruited from multiple sources. First, we will recruit among the 30 participants who previously enrolled in the Alpha-1 extension of the MESA COPD Study over the telephone (AAAD6395). All of these participants agreed to be contacted for future research purposes on their consent forms. Second, we will email,

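### Section 1 says success would demonstrate AAT benefit, but off-AAT status coincides with the last visit for every participant, so the planned paired t-test cannot separate it from study time

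*Combined protocol and SAP*

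**What the plan says.** **Claim (Section 1).** "Successful completion of these aims would demonstrate that aspirin and AAT augmentation therapy improve pulmonary microvascular blood flow". The sentence goes on to the reduction in CD31+ EMPs and to further benefits of augmentation.

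**Design (Sections 1 and 2).** The AAT part is described as "a withdrawal study with a follow-up visit off AAT augmentation therapy". Randomisation applies to aspirin only: "Eligible patients will then be randomized as to the order of intervention vs. placebo". The blinding statement in 2.f sits in the same description: "subjects and the investigative team will be blinded as to treatment assignment". For AAT, 2.h says: "Subjects will be asked to stop AAT augmentation therapy for approximately 5 weeks and return for Visit 4". Table 1 labels Visit 4, and no other visit, "Off AAT augmentation". No visit after AAT is resumed is listed.

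**Analysis (Section 3.a).** The second primary comparison is a paired t-test of "EMPs on AAT augmentation therapy compared to off augmentation following the intention-to-treat principle". The on-AAT visit that enters the pair is not named. Evaluation of period and carryover effects is listed among the exploratory analyses.

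**The concern.** Randomised order and blinding support a causal reading of the aspirin comparison. The AAT comparison has neither, yet Section 1 uses the same causal verb for both. A paired test removes differences between people. It does not remove change over time within them, and here the change of condition and the passage of time happen together for everyone. Repeat testing follows study time by construction. Assay, scanner or seasonal drift adds to it to the extent that calendar time lines up with visit order.

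At stake is the reading of a significant on/off difference in CD31+ EMPs, the primary endpoint of the withdrawal study. The protocol's wording would present it as proof of benefit from augmentation, although the design could produce it with no AAT effect at all.

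A second ambiguity adds to this. Because 3.a names no on-AAT visit, the on-AAT value may come from the aspirin period, so the contrast could also carry an aspirin effect.

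**Working it through.** **1. The plan's own figure.** Section 3.b equates 0.30 log CD31+ EMPs with 1.2 SD, so the implied SD is 0.30/1.2 = 0.25 log. It comes from a cross-sectional analysis. A paired t-test with n = 15, 80% power and two-sided 5% detects 0.78 SD, or 0.78 × 0.25 = 0.19 log, so the stated 1.2 SD is not reproduced. That is a separate matter. Only the 0.25 log is used here, to convert units.

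**2. Visit and condition.** Weeks are assumed from 2.f and 2.h: about 2 weeks of treatment, then "There will be a 2-week washout period between the treatments", then about 2 weeks of treatment, then withdrawal starting straight after Visit 3. Figure 1 is not available.

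| Visit | Assumed week | AAT | Aspirin/placebo |
|---|---|---|---|
| 2 | 2 | on, everyone | randomised |
| 3 | 6 | on, everyone | the other one |
| 4 | 11 | off, everyone | neither |

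Let τ be the effect of stopping AAT and δ the mean change tied to study time. The paired difference has expectation τ + δ, less the aspirin effect if the on-AAT visit is the aspirin period. Visit 4 has no on-AAT observations, so τ and δ cannot be separated without assuming a time course.

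**3. Rejection rate when τ = 0.** Inputs: n = 15, df = 14, one on-AAT comparator visit, critical value 2.145, drift d in SDs of the paired difference. The statistic is noncentral t with parameter d√15.

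| d (assumed) | log EMPs at SD 0.25 | d√15 | Two-sided rejection | Opposite tail |
|---|---|---|---|---|
| 0 | 0 | 0 | 5% | 2.5% |
| 0.2 | 0.05 | 0.77 | 11.2% | 0.4% |
| 0.3 | 0.075 | 1.16 | 19.2% | 0.1% |
| 0.5 | 0.125 | 1.94 | 43.8% | <0.1% |

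Almost all of the excess lies in the direction of the drift. A rise at Visit 4 produces false benefit. A fall works against AAT, and false benefit then occurs at the opposite-tail rate.

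**4. Price of adjusting for linear time.** Take a model with participant effect, aspirin indicator and off-AAT indicator, sequences split 8 aspirin-first and 7 placebo-first, independent errors and SD of a paired difference equal to 1.

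- Without time, the off-AAT term compares Visit 4 with the placebo visit: SE = 1/√15 = 0.258.
- The slope comes from the crossover, as the average of the two sequence-specific Visit 3 minus Visit 2 means: SE = ½√(1/8 + 1/7) = 0.259 over 4 weeks, or 0.0647 per week.
- The mean placebo-visit time is (8×6 + 7×2)/15 = 4.13 weeks, so the extrapolation is 11 − 4.13 = 6.87 weeks.
- With time: SE = √(0.258² + (6.87 × 0.0647)²) = √(0.0667 + 0.1973) = 0.514, a ratio of 1.99.
- Cross-check with the simpler contrast (V4 − V3) − 1.25(V3 − V2): ratio √((1 + 2.25² + 1.25²)/2) = 1.95.
- Power at 0.78 SD: 0.78/0.514 = 1.5 on 45 − 15 − 3 = 27 df, about 31%, against 80% for the planned paired test.

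**The case against.** The strongest reply is that the protocol is open about the design. It calls this part a withdrawal study, keeps it apart from the randomised trial, and states its hypothesis as an on/off comparison. The sentence in Section 1 is rationale, not a reporting rule, in a 15-person Phase IIa study. Section 2.g ties visits to the infusion schedule to keep them comparable, and 7.a.iii expects little change in emphysema or exacerbations over the withdrawal period. Section 3.a does list period and carryover evaluation. All of this is accurate and keeps the point moderate. None of it separates AAT from time at Visit 4: the exploratory evaluation can estimate only the Visit 2 to 3 change, and nothing says it will be carried to the on/off contrast.

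A reader might infer more than the documents support:

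- *That all drift falls on the AAT contrast.* Drift between Visits 2 and 3 also enters the aspirin comparison as a period effect. If entry is staggered (an assumption; no dates are given), calendar drift need not line up with Visit 4.
- *That the false-positive rate is 11% to 44%.* The drift sizes are assumed, so the figures show sensitivity only.
- *That readers are unmasked.* Open-label status is itself inferred from the absence of a sham. It matters less for a laboratory count than for the walk test and questionnaires. Section 10 sends MRI data under acrostic and study ID only; whether readers know the visit is not stated.

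It is also fair to say that the adjusted model is weak: a non-significant adjusted result would tell little.

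**Conclusion.** The point holds for the AAT half of the Section 1 sentence. Off-AAT status is fully aliased with the last visit, so the comparison estimates a before-after change. A causal reading needs the added assumption of no study-time change. The aspirin half, randomised and blinded, is not affected.

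Under the stated assumptions (n = 15, no AAT effect, a single on-AAT comparator), modest drift is enough to matter: 0.05 to 0.125 log, well under the 0.30 log the plan aims to detect, gives 11% to 44% rejection. The conversion to log units rests on a cross-sectional SD. If the within-person SD is smaller, as 3.b expects, the same drift in log units is a larger fraction of it. The documents do not show that such drift exists, and they do not support calling the withdrawal data worthless. They support a narrower conclusion and a planned check.

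**What to change.** 1. **Section 1.** Keep the aspirin aim as a randomised test. Reword the AAT aim: a favourable result would be a before-after change consistent with an AAT effect, confounded with time, and would support a controlled study.
2. **Section 3.a.** Pre-specify a sensitivity model over Visits 2 to 4 with participant effect, aspirin indicator and off-AAT indicator, fitted with and without linear time in weeks. Report both off-AAT estimates beside the Visit 2 to 3 period estimate. The aspirin term keeps aspirin exposure out of the on-AAT value. State in advance that linearity beyond Visit 3 cannot be tested, that the SE about doubles (0.26 to 0.51 SD), and that the model informs interpretation without replacing the primary test.
3. **Sections 5 and 10.** Where feasible, code EMP samples and MRI exports so that visit number is hidden from readers. Hiding the date is not workable for EMPs, because Section 5 sends the syringe for analysis immediately.

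The cost is some rewording, one extra model on data already scheduled and a coding step. No visit, participant or treatment changes. The price to the sponsor is a less favourable claim and a wide interval in the time-adjusted analysis.

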- i. Aspirin 81 mg daily x 2 weeks. Aspirin is a commonly used over-the-counter medication that is generally regarded as safe. The most common adverse effects of aspirin are minor bleeding and gastrointestinal upset. Serious adverse effects are rare, but include intracranial and gastrointestinal hemorrhage. The increased attributable risk of intracranial hemorrhage for daily aspirin use (most at 81 mg, some at 325 mg dose) was 0.4 events per 1000 person-years, and attributable risk of gastrointestinal hemorrhage due to peptic ulcer disease was 2 events per 1000 persons-years.³⁶ Renal function can be transiently reduced with aspirin, as with any nonsteroidal anti-inflammatory drug, but this is rare in the absence of chronic kidney disease.³⁷ In AATD there is no documented increase in adverse effects of aspirin. However, those with cirrhosis or liver failure should avoid aspirin due to increased risk of variceal bleed³⁸ and acute kidney injury.³⁷ Aspirin will be administered for at least 2 weeks, and may be continued for up to 18 days if needed to coordinate scheduling for the participant and Visit 2 or 3 procedures.
- ii. Placebo daily x 2 weeks. There are no risks of the placebo medication. Participants will be asked not to take aspirin and other nonsteroidal anti-inflammatory drugs during the study period, but are able to take Tylenol if needed. We plan to exclude subjects who take aspirin prescribed by a physician, minimizing the potential risk of withholding a participant's usual medication. Placebo will be administered for at least 2 weeks, and may be continued for up to 18 days if needed to coordinate scheduling for the participant and Visit 2 or 3 procedures.
- iii. Stopping alpha-1 antitrypsin replacement therapy. Participants will be asked to stop AAT replacement therapy for 5 weeks, so that AAT levels drop to levels seen in the absence of AAT replacement. AAT replacement therapy may be withheld for up to 40 days if needed to coordinate scheduling for the participant and Visit 4 procedures. AAT replacement therapy is the standard of care for AATD in the U.S. and was FDA-approved because it was shown to restore AAT in the lung to normal levels.³⁹ Further evidence for its use is based mostly on observational data: an alpha-1 registry study compiling 5 years of data found a lower mortality in those on augmentation compared to those not, and a slower decline in FEV₁ in those with poor lung function

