on augmentation therapy compared to those not on augmentation therapy;⁴⁰ a meta-analysis of randomized and non-randomized studies found a slower rate of FEV₁ decline in those with initial FEV₁ between 30-65% predicted who were on augmentation therapy compared to those not on therapy;⁴¹ and a retrospective study found lower exacerbation rates and less severe exacerbations in subjects when they were on augmentation therapy compared to when they were not on augmentation therapy.⁴² A few RCTs have also found a borderline reduction in the progression of CT emphysema in those on AAT augmentation compared to those not,⁸⁻¹⁰ with one meeting statistical significance.¹¹ One of these RCTs evaluated exacerbations in 77 participants over 2 years, they found the overall exacerbation rate to be similar among the two groups, however a post-hoc analysis found a reduction in severe exacerbations (those requiring hospitalization) in those on augmentation therapy.⁹ In summary, there is no data to suggest that short term withdrawal of AAT augmentation will lead to a clinical change or exacerbation. The participants in this study will miss approximately 4 doses of AAT augmentation over approximately 5 weeks (5.5 weeks maximum), this is 1/24 of the 2-year duration of the RCT mentioned above and there would be little change in emphysema or exacerbation rates expected to occur during this interval. However, we will mitigate the potential risk of increased exacerbations during this short withdrawal period by excluding participants who have experienced frequent exacerbations (2 or more exacerbations in the last year).

b. Study Procedures

- i. Anthropometry, blood pressure and pulse oximetry. There are no direct risks or discomforts from participation in the anthropometry, blood pressure or pulse oximetry to measure oxygen saturation.
- ii. Questionnaires. There is minimal risk related to questionnaires, this involves the social-psychological risk from the inadvertent disclosure of confidential medical information. We guard against this by maintaining study information identified by study number only in a filing system separate from the name and address files.

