- viii. MRI Scanning. The MRI procedures do not expose participants to ionizing radiation. All subjects will be screened to exclude those with contraindications to MR, including those with pacemakers, aneurysm clips, cochlear implants or other implanted electronic devices. Subjects with a history of occupational exposure to small metallic projectiles will be further evaluated with orbital radiographs as needed. There is also a psychological risk if an individual becomes claustrophobic while inside the MRI machine. Claustrophobic episodes may be traumatic to the patient, however it resolves after removal from the scanner and usually does not have any known lasting effects. We minimize this risk by excluding subjects with a known history of severe claustrophobia. Subjects will be in direct verbal contact with the MRI operator at all times and MRI examinations will be terminated at any time upon the request of the subject. The MRI scanner areas at the sites are equipped with standard emergency equipment for a hospital-based MRI center.
- ix. Gadolinium (contrast agent). There is a risk of allergic reaction after the gadolinium injection; with less than one in 300,000 chances that this will severe. Metallic taste in the mouth, tingling in the arm, nausea, or headache occurs in less than 1% (less than 1 in 100) people. Insertion of the needle may also cause minor pain, bruising and/or infection at the site. Participants with chronic renal insufficiency (estimated glomerular filtration rate [eGFR] < 45 mL/min/1.73 m²) will be excluded to eliminate the risk of nephrogenic systemic fibrosis. Gadolinium has recently been reported to persist in the brain; the significance of this finding is unknown and there is no reported harm. Persistence of a gadolinium signal in the brain has been reported to be associated with renal failure, linear gadolinium agents compared to macrocyclic agents, and cumulative dose.^{43,44} We will guard against this potential harm by using a macrocyclic agent (gadoterate meglumine, Dotarem). The macrocyclic agents are not reported to persist in the brain,^{45,46} and we use a very low dose so that our cumulative study dose of 0.09 mmol/kg is less than the clinical dose for 1 scan of 0.1 mmol/kg. We will also exclude those who have received gadolinium agents within the past 6 months.

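### Two exclusion limits are printed in the wrong units, and the maximum AAT interruption is 5.5 weeks in two places but 40 days in a third

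*Combined protocol and SAP*

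**What the plan says.** **Platelets.** The first exclusion criterion, section 2.d.i, begins "Platelet count < 150,000/dL". The protocol states no other platelet limit.

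**Renal function.** Section 2.d.v excludes chronic renal insufficiency, defined by "estimated GFR < 45 L/min/1.73" m². Section 7.b.ix (gadolinium risk) restates the exclusion as "glomerular filtration rate [eGFR] < 45 mL/min/1.73" m².

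**Use of these limits.** Under section 2.f, at Visit 1 and after consent, "a platelet count and creatinine will be drawn to confirm eligibility". Randomization to the order of aspirin and placebo follows.

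**AAT interruption.** Three sentences give a maximum:

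- Section 2.h: "Withdrawal of AAT for 5 weeks (a maximum of 5.5 weeks").
- Section 7.a.iii, early: "AAT replacement therapy may be withheld for up to 40 days if needed to coordinate scheduling".
- Section 7.a.iii, near its end, on the missed doses: "over approximately 5 weeks (5.5 weeks maximum").

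Section 7.a.iii also says of the treatment being withheld: "AAT replacement therapy is the standard of care for AATD in the U.S".

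**The concern.** The two laboratory limits decide who may be randomized, and as printed they fail in opposite directions.

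The platelet limit fails on the unsafe side. Applied literally, it removes nobody before an antiplatelet drug is given. The other bleeding-related exclusions in 2.d.i still apply: earlier intracranial or serious gastrointestinal bleeding, anticoagulants, prescribed antiplatelet drugs and known severe liver disease.

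The GFR limit fails on the safe side. Applied literally, it would stop all enrolment and could not expose anyone to gadolinium.

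The AAT figure limits how long participants go without a treatment that the protocol itself regards as standard. With two different maxima, the text does not settle whether a late Visit 4 is a protocol deviation.

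**Working it through.** Only unit conversion is needed. No sample-size, power or alpha figure enters.

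**1. Platelets (2.d.i)**

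- Input: 150,000 per dL.
- 1 dL = 100,000 µL, so 150,000 / 100,000 = 1.5 platelets per µL.
- Ratio to the presumed intended limit of 150,000 per µL: 150,000 / 1.5 = 100,000.

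A limit of 1.5 per µL excludes nobody. A micro sign lost when the PDF was read would leave a count per litre, not per decilitre, so a dropped character is an unlikely explanation.

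**2. GFR (2.d.v against 7.b.ix)**

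- Input from 2.d.v: 45 L/min/1.73 m². 45 × 1,000 = 45,000 mL/min/1.73 m².
- Input from 7.b.ix: 45 mL/min/1.73 m².
- Ratio: 45,000 / 45 = 1,000.

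The two sections state the same exclusion with units 1,000-fold apart, and 7.b.ix shows which is meant.

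**3. Maximum AAT interruption (2.h and 7.a.iii)**

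The protocol prints weeks in two places and days in the third; the other unit in each row is a conversion.

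| Place | Printed | Days | Weeks |
|---|---|---|---|
| 2.h | 5.5 weeks | 5.5 × 7 = 38.5 | 5.5 |
| 7.a.iii, early | 40 days | 40 | 40 / 7 = 5.71 |
| 7.a.iii, near its end | 5.5 weeks | 5.5 × 7 = 38.5 | 5.5 |

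- Gap between the maxima: 40 − 38.5 = 1.5 days.
- Planned interruption: 5 × 7 = 35 days.
- Scheduling slack: 38.5 − 35 = 3.5 days under one limit, 40 − 35 = 5 days under the other.

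The 40-day limit does not follow from the 5.5-week limit. A visit on day 39 or 40 meets the first and breaks the second.

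**The case against.** The strongest reply is that nobody would be misled.

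- **Platelets.** A limit of 1.5 per microlitre is not one that staff could sensibly apply, so they would read it as per microlitre. The other exclusions in 2.d.i still give protection. The telephone Screening Questionnaire also checks eligibility, but its wording is not in the document, so it cannot show how the limit is applied.
- **GFR.** The protocol resolves this itself in 7.b.ix, and 2.d.v names the MDRD equation, which leaves no room for 45 litres per minute. A letter may also have been lost when the PDF was read.
- **AAT interruption.** Forty days is 5.71 weeks, which rounds to 5.5 at the nearest half week, so the two figures may be one limit stated roughly and then precisely. On weekly dosing, counted from the last infusion, scheduled doses fall on days 7, 14, 21, 28, 35 and 42. None falls between day 38.5 and day 40, so the discrepancy costs no further dose.

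Most of this stands as an argument about weight, and it keeps the point minor. It does not remove the errors. For platelets the intended limit has to be guessed, because there is no second statement. For GFR the possible reading artefact is a good reason to look at the source file first; if the letter is there, that part falls away and the other two remain. For AAT, all three sentences set an upper limit, and an upper limit rounded down is a stricter one, so the status of day 39 or 40 remains open.

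**Conclusion.** The point holds, as a minor one. The platelet limit is wrong as printed by a factor of 100,000 and carries most of the weight, because it is used before aspirin and nothing else in the protocol corrects it. The GFR limit in 2.d.v differs from 7.b.ix by a factor of 1,000, subject to a check of the source file. The maximum AAT interruption differs by 1.5 days between statements, two of which are in the same subsection.

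The practical effect is small on the assumption that staff read both units as intended. That 150,000 per microlitre was meant is also an assumption, though an easy one. Sample size, power and the planned paired analyses do not depend on any of these figures.

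**What to change.** - **2.d.i:** restate the platelet limit per microlitre, presumably < 150,000/µL, with the investigator confirming the value.
- **2.d.v:** check the source file; if it also prints litres, change the unit to mL/min/1.73 m² to match 7.b.ix.
- **2.h and both sentences in 7.a.iii:** choose one maximum in whole days and use it in all three places. Thirty-eight days stays within 5.5 weeks. If 40 days is wanted for scheduling, replace the 5.5-week figure in 2.h and in the later sentence of 7.a.iii.

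The cost is a short editorial amendment to 2.d.i, 2.d.v, 2.h and 7.a.iii, with no change to sample size, power or analysis.
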